9.0 Procedures Involved*

This is an unblinded randomized controlled crossover trial to examine whether 3 weeks of light alcohol consumption causes a short-term change in sex hormone levels compared to levels following 3 weeks of white grape juice consumption among postmenopausal women with estrogen receptor-positive (ER+) breast cancer taking an aromatase inhibitor. In this design, participants are compared to themselves at different times, with the sequence of the two treatment arms assigned by randomization. In other words, half of the women will be randomized to consume one serving of white wine every day for three weeks followed by one serving of white grape juice every day for three weeks, and half of the women will be randomized to three weeks of white grape juice followed by three weeks of white wine. To prevent a potential carryover effect of the drink in the first period affecting hormone levels in the second treatment period, we will ask participants to refrain from drinking any alcohol or grape juice for two weeks before starting each treatment arm. The women will know when they are supposed to drink the wine and when they are supposed to drink the grape juice.

Recruitment:

We will present the trial protocol and eligibility criteria at a meeting for the six medical oncologists and three nurse practitioners who provide outpatient care at the BIDMC BreastCare Center and ask for their assistance to recruit patients from their practice who may be eligible and interested in participating in our trial.

We will review medical records for patients receiving care in the BreastCare Center or Healthcare Associates (HCA), BIDMC's primary care practice, to see if they meet the eligibility criteria, and contact their health provider about their fitness to participate. Unless their provider recommends otherwise, we will mail an invitation letter to patients who appear to be eligible and ask them to contact us if interested. If they do so and remain interested, we will arrange a screening visit. We will also call participants who have received letters and have upcoming clinical appointments to remind them of the study and to determine if they would like to arrange a screening visit in conjunction with that appointment. We will also continue to place flyers and brochures in the BreastCare Center so that women who are interested in the study can reach out to us.

We are submitting a request for a waiver of HIPAA authorization to obtain protected health information for potentially eligible women receiving care at the BIDMC BreastCare Center to confirm eligibility. Institutions will register eligible

participants in the Clinical Trials Management System (CTMS) OnCore as required by DF/HCC Policy REGIST-101.

Screening Visit:

If a referred patient is interested in learning more about the study, we will invite her to meet with a member of the research team in a private room at the BIDMC BreastCare Center. The study team member will explain the study, obtain informed consent, and confirm eligibility. An MD is not required for the consent process. No study procedures will be performed prior to obtaining informed consent. If the patient has not had liver function measured in the past 12 months, we will conduct a liver function test at their screening visit. If a hemoglobin A1c or fasting glucose test is not available, we will refer them to their physicians until we can document clinical control. We will obtain information on medical history, including an assessment of their usual frequency of alcohol consumption (using the Alcohol use Disorders Identification Test (AUDIT), the type of aromatase inhibitor therapy prescribed, and demographic and medical characteristics,

Aromatase inhibitors are only prescribed to women who are postmenopausal, either naturally or artificially induced. If any women report that they are pre-menopausal, sexually active, and not using an effective form of contraception, we will counsel them that these medications are teratogenic and they will be referred back to their providers. Participants found ineligible will be thanked for their time but they will not be invited for the baseline visit (Study Visit 1). Either the primary investigator ([name]) or another physician involved in the study will review the screening results to confirm eligibility. Eligible participants will begin a two-week run-in period in which they will refrain from alcohol and grape juice (washout period 1).

Study Visit 1 (Baseline):

If the participant confirms that she did not drink alcohol or grape juice for the past two weeks, she will return for visit 2 after fasting for 12 hours. The BIDMC CRC nurses will draw 100 mL (approximately 7 tablespoons) of blood for real-time processing of a basic metabolic panel and safety monitoring (complete blood count and hepatic panel). We will store the remaining sample for analyzing sex hormone levels as soon as all participants complete the study. The CRC nurses will conduct the blood draw, specimen processing, and transportation to Quest Diagnostics in accordance with their pre-specified procedures.

The CRC research nurses will conduct safety monitoring at each study visit. Using their standard protocols, they will perform repeated measurements of vital signs, including height (at baseline), weight, systolic and diastolic blood pressure, and heart rate. They will measure supine blood pressure as the average of the final 2 of 3 measurements following at least five minutes of rest using an automated cuff device calibrated at least monthly. They will measure weight with the participant wearing light clothing and standing on a digital scale with handrails.

Using the REDCap randomization module, we will randomly allocate women to a sequence of either white grape juice followed by white wine or to a sequence of white wine followed by white grape juice. One drinking period consists of 3 weeks of one serving (5 oz≈14 g alcohol) of white wine consumption daily and the other drinking period consists of 3 weeks of a calorically equivalent serving (6 ounces) of (alcohol-free) white grape juice. At the beginning of the white wine drinking period, the participants will receive one 3L box and one 500 mL box of Bota Box Chardonnay, a commercially available white wine that is 13% alcohol by volume for the three weeks of one serving (5 ounces) of white wine consumption daily. At the beginning of the white grape juice drinking period, the participants will receive one 96-ounce bottle and one 64-ounce bottle of Welch's 100% White Grape Juice for the three weeks of a calorically equivalent serving (6 ounces) of (alcohol-free) white grape juice each day. There will be no blinding of the alcoholic beverages; all participants will know when they have been randomized to drink the white wine and when they have been randomized to drink the grape juice.

After obtaining IRB approval, we will work with the CRC to finalize the plans to purchase, store and transfer the white wine and white grape juice to participants. We will distribute the three-week supply of wine or grape juice and a standardized labeled measuring cup to ensure that participants consume the correct amount each day. We will give the participants an information sheet, advising them to refrain from all alcohol and grape juice except their assigned drink and to maintain their typical patterns of diet and activity throughout the study. For the three weeks of white wine intake, we will advise participants to drink their daily serving at a time when they will not drive or operate machinery in subsequent hours. We will also provide a paper calendar for participants to record their daily alcohol and grape juice intake and tell them that we will review this calendar with them on our weekly phone calls.

Study Visit 2:

At the end of the 3-week drinking period, the participant will come to the BIDMC CRC, and a nurse will draw 90 mL (approximately 6 tablespoons) of blood for safety measures and sex hormone levels. They will also take vital signs and measure weight. We will ask participants to bring leftover drinks to this visit so that we can measure the remaining amount as an indicator of adherence. We will ask participants to refrain from drinking any alcohol or grape juice for the next two weeks (washout period 2).

Study Visit 3:

At the end of the 2-week washout period, the participant will come to the BIDMC CRC, and a nurse will draw 90 mL (approximately 6 tablespoons) of blood for safety measures and sex hormone levels. They will also take vital signs and measure weight. We will then distribute the second beverage to consume daily for the following 3 weeks.

Study Visit 4:

At the end of the 3-week drinking period, the participant will come to the BIDMC CRC, and a nurse will draw 90 mL (approximately 6 tablespoons) of blood for safety measures and sex hormone levels. They will also take vital signs and measure weight. We will ask participants to bring leftover drinks to this visit so that we can measure the remaining amount as an indicator of adherence.

Blood Samples: The nurse will obtain blood samples in the morning after the last day of each 2-week washout period and each 3-week dietary period. We will schedule blood draws for time windows of up to ± 4 days of the end of the prior washout or drinking period. If the visit is delayed for up to four days, we will ask participants to continue the protocol (washout, white wine, or white grape juice) for the additional days. At visit 1, the nurse will draw 100 mL (approximately 7 tablespoons) of blood and at visits 2, 3, and 4, the nurse will draw 90 mL (approximately 6 tablespoons) of blood. They will draw one 10 mL tube for each of the 10 assays: complete blood count, hepatic function panel, basic metabolic panel (only at visit 1), DHEAS, FSH, LH, SHBG, estradiol, testosterone, and progesterone. This amount is in accordance with the BIDMC Committee on Clinical Investigations (CCI) Blood Volume Safety Guidelines.

The CRC staff will centrifuge the blood samples for the complete blood count, hepatic function panel, basic metabolic panel, and sex hormones for 15 min at 2000x g and 4°C between 15 and 30 min after collection. They will aliquot the plasma and serum in labeled 250 μ l cryovials and store the samples at -80°C in CRC freezers. The CRC will send blood samples to Quest Diagnostics. The safety measurements will be conducted within 72 hours of collection. At the end of the study, they will send frozen samples from each visit to Quest Diagnostics for analysis of sex hormones. The CRC nurses will conduct the blood draws, specimen processing, and transfer to Quest Diagnostics in accordance with the CRC's established protocols to maintain the quality of the specimens and to protect the privacy of the participants.

Safety and Adherence: A member of the research team will call participants once per week to ask about any changes in health, to remind the participant to complete the weekly online questionnaire about lifestyle factors, and to address any questions that they may have about their participation in the study. A safety monitor will oversee patient safety by regularly monitoring participants' vital sign and body measurements from clinic visits, lab results for liver function, complete blood count, and triglycerides and responses to questions from the weekly check-in calls about any changes in health, and they will follow up with any participant whose results are concerning.

We will assess adherence by asking participants to return unused drinks so that we can measure how many drinks the participant consumed, at least from the provided drinks. Throughout the ten weeks of the trial, participants will complete weekly REDCap online questionnaires about lifestyle factors over the prior week. We will also ask participants about their alcohol intake. Depending on participant preference

and feasibility, participants may report daily alcohol intake using the REDCap alcohol timeline follow-back assessment or they may opt to respond to a daily REDCap-secured survey that will be texted to them every evening. If participants report more than the assigned amount of wine during any study visit including the final visit, on a questionnaire, or during a phone call with study staff, [name] will speak with them to determine if any evidence of alcohol use disorder or at-risk drinking is present, and all such participants will be referred for counseling. Those with no such evidence of problem drinking will remain in the study with continued monitoring.

As an objective marker of alcohol adherence, we will pool some of the remaining blood samples across participants. After the sex hormone analyses are complete, the staff at the Brigham Research Assay Core who conducted the sex hormone analyses will one pooled sample from several participants following the wine phase and one pooled sample from several participants following the grape juice phase. We will send the two samples to Quest Diagnostics to estimate average phosphatidyl ethanol levels as an objective marker of adherence to the study protocol—the average phosphatidyl ethanol levels by treatment period across several individuals, with no individual results for each participant. The purpose is to estimate an objective marker of alcohol adherence, and not to test any new scientific hypotheses. We plan to report the average phosphatidyl ethanol levels in our findings on the study.

To minimize risk, we have established clear and conservative entry criteria for interested participants. In particular, we require that all participants are current drinkers and that they typically consume at least one alcoholic drink per week but no more than two servings per day. This level, and the intervention dose of one drink per day, are explicitly within the limits of consumption for women diagnosed with breast cancer established by the American Society of Clinical Oncology.

We will establish a formal safety monitor. This role may be filled by [name] or by a breast cancer specialist to whom he may delegate this role. The safety monitor will oversee patient safety by regularly monitoring participants' lab results and responses to questions from the weekly check-in calls about any changes in health. They will assess the severity, expectedness, and relationship to the intervention for any self-reported symptoms or lab results and document adverse events. In addition, we will set up an independent data safety and monitoring board (DSMB) that will meet every 6 months to evaluate the safety and utility of continuing the pilot trial.

If a participant experiences an adverse event, she will be directed to her treating oncologist. We will also notify the IRB, as appropriate (see section 12).

We aim to assure data quality and protect the confidentiality of participant data by using REDCap electronic data capture tools. REDCap (Research Electronic Data Capture) is a secure, web-based application designed to support data capture for research studies.

We are submitting drafts of the study materials with this application for protocol approval, and we will convert these data collection tools to forms in the REDCap database.

Screening Eligibility Checklist: The study staff will complete this measure with the participant during the screening visit and by reviewing medical records. This assessment includes the Alcohol Use Disorders Identification Test (AUDIT). At the screening visit, we will also collect contact information.

Clinical Research Center Visit form: We will collect information about anthropomorphic data, blood samples, and responses to questions about medical history, lifestyle factors, alcohol intake, and changes in medications during the study.

Weekly Check-In Call: The study staff will call participants once per week and ask them if they “had any reason to speak to or visit your health practitioner since we last spoke?” If the participant responds that there have been reasons to seek care, the study staff will ask for details. The study staff will also ask if “there any other changes to your health that you want us to know about?” and if the participant reports any changes, the study staff will ask for details. This information will be relayed for the safety monitor to review in the secure REDCap system. We will use the structure of the alcohol timeline follow-back survey to assess daily alcohol and grape juice intake since the prior check-in call. We will ask participants to record their daily intake on their paper diary that we gave them at Visit 1.

Weekly REDCap Survey: Participants will complete an online weekly survey through the REDCap system. If they would prefer to complete this survey by phone, a member of the study staff will conduct this survey as an interview by phone and enter the data into REDCap on the participant’s behalf. The survey also includes the short version of the Centre for Epidemiological Studies Depression Scale (CES-D 10), a Pain Intensity Scale using a visual analog scale to rate overall pain from 0 to 100, and in two of the weekly assessments, participants will complete the Pittsburgh Sleep Quality Index (PSQI) about their sleep quality over the prior month.

As indicated in the table of assessment times below, we will collect information about eligibility at the screening visit, and at visits 1, 2, 3, and 4, we will collect information about body measurements, vital signs, blood samples, and alcohol intake. In the weekly questionnaires, participants will provide information about alcohol intake, lifestyle factors, and any concerns. We will schedule blood draws for time windows of up to ± 4 days of the end of the prior washout or drinking period. If the visit is delayed for up to four days, we will ask participants to continue the protocol (washout, white wine, or white grape juice) for the additional days. Similarly, we will schedule weekly calls for up to 4 days before or 4 days after the target schedule date.

		Screening	Washout 1	Washout 1	Visit 1	Drinking Period	Drinking Period	Drinking Period	Visit 2	Washout 2	Washout 2	Visit 3	Drinking Period	Drinking Period	Drinking Period	Visit 4	# Assessments
Study Day	0	1-7	8-14	15	15-21	22-28	29-35	36	36-42	43-49	50	51-57	58-64	65-71	72		
Window Allowance (Days)		±4	±4	±4	±4	±4	±4	±4	±4	±4	±4	±4	±4	±4	±4		
Type of Visit	Clinic	Phone	Phone	Clinic	Phone	Phone	Phone	Clinic	Phone	Phone	Clinic	Phone	Phone	Phone	Clinic		
Payment					\$20				\$30			\$30				\$50	
Admin, Body Measurements, and Vitals																	
Consent, contact information		X															1
Eligibility: e.g., Alcohol use Disorders Identification Test (AUDIT) and hepatic panel if none in the past 12 months*		X															1
Randomization			X														1
Verification of consent and documentation			X						X		X				X		4
Height			X														1
Weight, waist circumference			X						X		X				X		4
Vital signs- blood pressure, heart rate			X						X		X				X		4
Distribute drink			X								X						2
Measure leftover drink									X						X		2
Pay participant, reimburse parking			X						X		X				X		4
Blood Draw																	
Hepatic panel	*		X						X		X				X		4
Complete blood count with differential			X						X		X				X		4
Basic metabolic panel (fasting)			X														1
Lipid panel										X					X		2
Estradiol and estrone			X						X		X				X		4
Sex hormone binding globulin (SHBG)			X						X		X				X		4
Dehydroepiandrosterone sulfate (DHEAS)			X						X		X				X		4
Testosterone			X						X		X				X		4
Weekly Call																	
Health events		X	X		X	X	X		X	X	X	X	X	X	X		10
Other health changes		X	X		X	X	X		X	X	X	X	X	X	X		10
Alcohol and grape juice timeline follow-back		X	X		X	X	X		X	X	X	X	X	X	X		10
Weekly REDCap Questionnaires																	
Pittsburgh Sleep Quality Index (PSQI)									X						X		2
Depressive Symptoms (CES-D-10)		X	X		X	X	X		X	X	X	X	X	X	X		10
Overall pain (visual analog scale)		X	X		X	X	X		X	X	X	X	X	X	X		10
Open text-any questions, concerns, comments		X	X		X	X	X		X	X	X	X	X	X	X		10

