Our primary endpoint is free estradiol (estradiol divided by SHBG). We should have excellent power to assess effects of alcohol on DHEAS but reasonable power to detect effects on estrone sulfate, although, as a pilot study with an intentional goal of training and career development, power is but one dimension on which to evaluate the merits of the trial. We have used standard formulae to estimate the minimum detectable difference for 2-period crossover trials (http://hedwig.mgh.harvard.edu/sample_size/js/js_crossover_quant.html). Using the 4-week results of a similar crossover trial of alcohol on changes in estrone sulfate and DHEAS, and using the dosage of 15 gm/day that most closely approximates the dosage proposed in this application, we can estimate the proportional changes anticipated with varying degrees of power, as shown below at a two-sided 0.05 significance level. Based upon data presented in that trial, we estimate the SD of within-person differences to be 42% for estrone sulfate and 13% for DHEAS.

Power	Minimum Detectable Difference	
	Estrone sulfate (ng/dl)	DHEAS (ng/dl)
50%	19%	6%
80%	28%	9%
90%	32%	10%

For comparison, the increases in estrone sulfate in previous trials of alcohol were 15-21% in a trial of premenopausal women and 7-22% in a trial of postmenopausal women.

The comparable effects on DHEAS were 4-7% and 5-9%. Thus, we appear to have adequate power to detect effects of the expected size from previous crossover trials. Moreover, we have particularly strong power to exclude virtually all clinically significant increases (e.g., increases of 10% or larger) in DHEAS.

Our results would also provide all necessary information to power a more definitive trial of estrone and other estrogens.

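### Three separate small inconsistencies in Section 9.0 need reconciling: wine supply against the late-visit rule, grams against stated strength, and early visits against the second two-week washout

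*Combined protocol and SAP*

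**What the plan says.** All references are to the combined protocol and SAP.

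- **Supply and serving (Section 9.0, Study Visit 1).** The wine period is "3 weeks of one serving (5 oz≈14 g alcohol) of white wine consumption daily". For it, "the participants will receive one 3L box and one 500 mL box of Bota Box Chardonnay", described as "a commercially available white wine that is 13% alcohol by volume". The juice period uses 6 oz daily from one 96 oz and one 64 oz bottle. Section 9.0 calls each quantity a three-week supply.
- **Window (Section 9.0, Blood Samples, repeated before the assessment table).** Draws may fall up to 4 days before or after the end of the preceding washout or drinking period. For late visits, "we will ask participants to continue the protocol (washout, white wine, or white grape juice) for the additional days". No rule is given for early visits.
- **Washout (Section 9.0, opening paragraph).** To prevent carryover, participants are asked to "refrain from drinking any alcohol or grape juice for two weeks before starting each treatment arm". The Study Visit 1 text makes confirmed two-week abstention a condition of going on. The Study Visit 3 text, where the second beverage is handed out, has no matching condition.
- **Dose reference for power (Section 11.0).** The detectable differences were derived "using the dosage of 15 gm/day that most closely approximates the dosage proposed in this application".
- **Access check (Section 11.0).** The weekly call is meant, among other things, to confirm that participants still have their drinks.

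**The concern.** The three points are independent of one another.

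1. The late-visit rule asks for up to 25 daily servings, and the wine handed out does not stretch that far. The juice does, so any shortfall arises in the wine phase only and falls immediately before the endpoint draw. The plan also does not say how a wine period that ran out would be classed in the per-protocol analysis of Section 11.0.
2. The dose is the defining feature of the intervention. The gram figure, serving volume and strength in the same paragraph do not agree, so a reader cannot tell what daily dose was intended.
3. Washout 2 is the interval that separates the two beverages, and Section 9.0 relies on its two-week length to prevent carryover. The early side of the window lets it be shorter, and the mixed model in Section 11.0 does not use actual washout or drinking days.

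**Working it through.** **Inputs from the documents.** Serving 5 oz; stated alcohol about 14 g; strength 13% by volume; wine 3,000 + 500 = 3,500 mL; juice 96 + 64 = 160 oz at 6 oz per day; window ±4 days; stated periods 21 and 14 days.

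**Assumptions not in the documents.** US fluid ounce 29.57 mL (range tried 28.41 to 30 mL); ethanol density 0.789 g/mL (range 0.785 to 0.794).

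**1. Supply**

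One serving = 5 × 29.57 = 147.87 mL. Servings supplied = 3,500 / 147.87 = 23.7. Volume needed = days × 147.87 mL.

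| Drinking days | Needed (mL) | Supplied minus needed (mL) |
|---|---|---|
| 21 (on time) | 3,105 | +395 |
| 23 (+2) | 3,401 | +99 |
| 24 (+3) | 3,549 | −49 |
| 25 (+4) | 3,697 | −197 |

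The plan's description of a three-week supply is therefore confirmed, with 395 mL to spare. At +3 days the gap is 49 / 147.87 = 0.33 of a serving. At +4 days it is 197 / 147.87 = 1.3 servings.

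Juice: 160 / 6 = 26.7 servings. Twenty-five days need 25 × 6 = 150 oz, so 10 oz remain.

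Sensitivity to the ounce:
- At 28.41 mL, 25 days need 3,552 mL (52 mL short). Twenty-four days need 24 × 142.07 = 3,410 mL, which the supply covers.
- At 30 mL, 25 days need 3,750 mL (250 mL short).

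The +4-day shortfall holds throughout; the +3-day shortfall depends on the ounce.

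**2. Alcohol per serving**

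Grams = volume × strength × density = 147.87 × 0.13 × 0.789 = 15.17 g, and 15.17 / 14 = 1.083, about 8% above the stated figure. Across the ranges the result is 14.5 to 15.5 g. The stated 14 g is reproduced at a strength of 14 / (147.87 × 0.789) = 12.0%. Over 21 days the two figures give 21 × 14 = 294 g and 21 × 15.17 = 318.5 g.

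Check on power: the minimum detectable differences were recomputed for 20 women (noncentral t, 18 df, scale SD/√20) from the stated within-person SDs of 42% and 13%.

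| Power | Estrone sulfate: stated / recomputed | DHEAS: stated / recomputed |
|---|---|---|
| 50% | 19% / 19.4% | 6% / 6.0% |
| 80% | 28% / 27.8% | 9% / 8.6% |
| 90% | 32% / 32.2% | 10% / 10.0% |

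The table reproduces. The gram label does not enter it, and 15.2 g is close to the 15 g/day reference.

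**3. Early visits**

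Drinking period: 21 − 4 = 17 days (17/21 = 81% of the stated length). Washout 2: 14 − 4 = 10 days (10/14 = 71%). Washout 1 is protected by the abstention condition at visit 1.

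**The case against.** There is a good case that little is at stake.

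- **Supply.** It is adequate for the planned three weeks and for delays of up to 2 days. The weekly call checks access to drinks, and Section 9.0 leaves purchase and transfer arrangements to be finalized with the research center. This stands as mitigation, but no passage states a re-supply.
- **Bias.** A reader might infer that running out biases the trial toward no effect, the result hypothesized in Section 1.0. The documents do not support that. A woman delayed by 4 days who misses no earlier serving has still drunk 23.7 servings, more than the 21 of the planned period. Only recency changes: part of a serving on day 24 and none on day 25. The plan gives no frequency of such delays and no basis for quantifying an effect on the hormones.
- **Adherence.** A reader might also infer that leftover volume no longer measures adherence. It does: the volume supplied is known, so consumption from it is supplied minus returned. Section 9.0 already limits the measure to the provided drinks and adds a daily calendar and timeline follow-back.
- **Grams.** The figure is marked as approximate and no analysis uses it; Section 8.0 defines the contrast in servings. This stands as a limit on importance, but the figures in that paragraph still do not agree.
- **Window.** It is a declared tolerance and applies to both beverages alike. That is fair, but it does not remove the conflict with a two-week washout stated as the safeguard against carryover.

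**Conclusion.** The concern holds as three minor inconsistencies.

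1. With US ounces, the wine covers delays of up to 2 days and is 49 mL short at +3 and 197 mL short at +4. The juice covers the full window. Any effect is limited to the last one or two days before a late wine-phase draw and is probably small.
2. Five ounces at 13% gives about 15.2 g (14.5 to 15.5 g), not about 14 g. This is a labelling inconsistency with no effect on the power table.
3. An early visit allows 17 drinking days and about 10 days of washout 2.

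Two wider readings of the third item should be avoided. The shortened washout is not general, because abstention for two weeks is confirmed at visit 1. Applying ±4 days to the nominal study days in the assessment table (visit 2 on day 36, visit 3 on day 50) would give (50 − 4) − (36 + 4) = 6 days. However, the text ties the window to the end of the preceding period, so about 10 days is the figure to use. Nothing in the documents shows that 10 days is too short to prevent carryover; the point is only that it differs from the length the plan relies on.

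The arithmetic is secure under the stated conversions. The consequences for the hormone results are not quantified.

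**What to change.** - Reconcile the wine volume with the late-visit rule, so that both describe the same longest drinking period, and state whether re-supply is possible.
- Make the gram figure, serving volume and alcohol percentage agree.
- Reconcile the early side of the visit window with the two-week length of washout 2, and say what applies when visit 3 is early.
- From the daily intake records and draw dates already collected, derive actual drinking days, date of last serving and actual washout 2 days. Use them in a sensitivity analysis of the main mixed model, and state how periods in which the wine ran out are classed.

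The cost is protocol wording, possibly a small extra volume of wine, and a few derived variables. No new data collection is needed. Which serving size, supply or schedule is right is for the investigators to decide.
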